- 2) If at the end of the second intervention deployment (total of 20 patients randomized), the primary outcome improves (PaO₂/FiO₂ ratio at 48 hours) by $\geq 20\%$, or the secondary outcomes PaO₂/FiO₂ ratio at 24 hours improves $\geq 20\%$, or dead space decreases by 15%, or ICU- or ventilator-free days continue to exhibit a positive response (at least 2 days difference), we will modify the mode of administration of the second dose of tPA as follows: following the 50mg tPA bolus, we will initiate a drip of 2 mg/hr tPA over the ensuing 24 hours (total 48 mg infusion) accompanied by an infusion of 500 U/hour heparin during the tPA drip. After this, heparin dose will be increased slowly to maintain a PTT between 60 and 80 sec, titrated per attending's discretion. Interim analyses will be conducted as planned above, and submitted expeditiously to the DSMB, IRB and FDA for approval, yet enrollment will continue while these agencies deliberate and their feedback is received.

See above for the rationale for the tPA50+drip.

Statistical analysis (see attached Statistical Analysis Plan):

All analyses will be conducted initially as an intent-to-treat (patients are analyzed in the group they were randomized to), followed by an as-treated analysis. We will use linear mixed models (continuous outcomes, appropriate transformations if residuals normality departure is detected) or generalized estimating equations (categorical outcomes) to account for intra-hospital cluster effects and repeated measures, with FINAL (OVERALL) significance at $p < 0.05$ (two-tailed tests). If the groups are not comparable, we will compare relative (as opposed to absolute improvement over baseline (with patients as their own controls) to minimize the effect of baseline disparities. In addition, as the sample permits, we will adjust for confounders using a single propensity score adjustor in an inverse probability weighting approach. In addition, we will compare the "dose" of the intervention (i.e., how much of the treatment the patient received) as the effect of interest. The pre-planned final comparisons include within group (improvement over baseline) and between groups, all two-tailed with significance declared according to the alpha defined above by the Pocock spending method.

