### **Exclusion Criteria (At the Time of Enrollment)**

1. Active bleeding
2. Acute myocardial infarction or history of myocardial infarction within the past 3 weeks or cardiac arrest during hospitalization
3. Hemodynamic instability with Noradrenaline >0.2mcg/Kg/min

4. Acute renal failure requiring dialysis
5. Liver failure (escalating liver failure with ALT > 3 times baseline)
6. Suspicion of cirrhosis due to history of cirrhosis diagnosis, hepatic encephalopathy, documentation of portal hypertension, bleeding from esophageal varices, ascites, imaging or operative finding suggestive of liver cirrhosis, or constellation of abnormal laboratory test results suggestive of depressed hepatic function
7. Cardiac tamponade
8. Bacterial endocarditis
9. Severe uncontrolled hypertension defined as SBP > 185 mmHg or DBP > 110 mmHg
10. CVA (stroke), history of severe head injury within prior 3 months, or prior history of intracranial hemorrhage
11. Seizure during pre-hospital course or during hospitalization for COVID-19
12. Diagnosis of brain tumor, AVM or ruptured aneurysm
13. Is currently on ECMO
14. Major surgery or major trauma within the past 2 weeks
15. GI or GU bleed within the past 3 weeks
16. Known bleeding disorder
17. P2Y12 receptor inhibitor medication (anti-platelet) within 5 days of enrollment
18. Arterial puncture at a non-compressible site within the past 7 days
19. Lumbar puncture within the past 7 days
20. Pregnancy
21. INR > 1.7 (with or without concurrent use of warfarin)
22. Platelet count <  $100 \times 10^9/L$  or history of HIT
23. Fibrinogen < 300 mg/dL
24. Known abdominal or thoracic aneurysm
25. History of CNS malignancy or CNS metastasis within past 5 years
26. History of non-CNS malignancy within the past 5 years that commonly metastasizes to the brain (lung, breast, melanoma)

**5.3. Reasons and details of withdrawal:** the data will be presented and compared between the study groups.

**5.4. Baseline patient characteristics:** patients in the study groups will be compared regarding demographic characteristics, comorbidities, previous and current medications, presence of infectious and non-infectious complications, mechanical ventilation variables, and function of the central nervous, pulmonary, renal, liver, cardiovascular, inflammatory, coagulation and hematological systems.

**5.5. Multicenter description:** we will report the enrollment, withdrawal and outcomes of each participating hospital.

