## Section 6: Analysis of outcomes

### 6.1. Primary and Secondary Outcomes: see above

**6.2. Any calculation or transformations used to derive the outcomes:** all outcomes will be examined for distribution. If very skewed, we will attempt log and Box-Cox power transformations to approximate normality. If those are unsuccessful, the outcomes will be categorized using the median or previously defined cutoff (from literature). All outcomes will also be analyzed as change from baseline.

**6.3. Effectiveness of the randomization:** we will compare the study groups regarding above variables to determine baseline comparability of the groups. Per the CONSORT statement, p-values should not be used, as any differences are, by definition, by chance. We will use the absolute standardized mean difference (SMD)  $\leq 0.20$  to acceptable balance. Any differences deemed clinically relevant or with absolute SMD  $> 0.2$  will be adjusted for using inverse probability weighting methods as described below.

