### 6.4. Outcomes comparison:

All analyses will be conducted initially as an intent-to-treat (patients are analyzed in the group they were randomized to), followed by an as-treated analysis. The primary outcome will be assessed within group and between groups. Differences in the primary outcome will be assessed using linear mixed models, with appropriate transformations if normality departure of residuals is detected. Linear mixed models allows us to adjust for potential confounders detected in the comparison of the groups at baseline using inverse probability weighting by a propensity score, the covariance structure, the repeated measures and the intra-hospital correlation (as this is a multicenter study). In addition, it tolerates missing observations. We will also compare percent change over baseline, using t-tests with the appropriate adjustment for heteroscedasticity if needed. Categorical outcomes will be compared using generalized estimating equations to account for confounders (as above), covariance structure and intra-hospital correlation. In addition, we will compare the “dose” of the intervention (i.e., how much of the treatment the patient received) as the effect of interest, as premature death is, unfortunately, expected. Survival analysis with inverse probability weighted Cox proportional hazards model and robust sandwich variance estimate with clustering for hospitals will be used for mortality and for survivor-bias outcomes censoring for death (e.g., thrombotic complication). As all outcomes are in-hospital, loss to follow-up is not likely. The pre-planned comparisons include within group (improvement over baseline) and between groups, all two-tailed with significance declared as defined by the Pocock spending method.

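### SAP 6.3 lets chance imbalance and an open-label judgement choose the propensity-weighting set, the Protocol's adjustment rule differs, and neither document says whether the weighted or unweighted result is held to the Pocock boundary

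*SAP*

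**What the plan says.** SAP 6.3 (Effectiveness of the randomization) starts from the position that "p-values should not be used, as any differences are, by definition, by chance". It takes an absolute SMD of at most 0.20 as acceptable balance. Any difference above that, or judged clinically important, "will be adjusted for using inverse probability weighting methods as described below".

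The variables to be screened are those of SAP 5.4, where "patients in the study groups will be compared regarding demographic characteristics, comorbidities, previous and current medications", followed by complications, ventilation variables and the function of eight organ or physiological systems. No number or final list is given.

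SAP 6.4 makes a linear mixed model the method for the primary outcome, with intention-to-treat (ITT) first and as-treated second. It says the model makes it possible to "adjust for potential confounders detected in the comparison of the groups at baseline using inverse probability weighting by a propensity score". It adds a t-test on percent change in all cases.

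The Protocol (Statistical analysis) has a different rule: "as the sample permits, we will adjust for confounders using a single propensity score adjustor in an inverse probability weighting approach". It also has a second response to imbalance: "If the groups are not comparable, we will compare relative (as opposed to absolute improvement over baseline". It gives no threshold for either.

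SAP 6.4 applies the boundary to within-group and between-group comparisons alike, with "significance declared as defined by the Pocock spending method". The Protocol says the same in substance. Neither document names baseline P/F as a model covariate. It enters through change, percent change and a subgroup.

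**The concern.** If baseline differences in a randomized trial arise by chance, a rule that adjusts for whichever differences turn out large lets chance choose the model. At this sample size the threshold of 0.2 is well inside the range that chance produces. The second route, clinical judgement, is exercised in an open-label trial with no prior list.

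Two things are at stake. First, the primary estimate depends on which imbalances occur, and the two documents respond to imbalance differently. Second, estimating weights from many variables in 50 patients can add variance, while baseline P/F, the obvious candidate predictor of 48-hour P/F, is adjusted for only when it happens to be imbalanced. The result also feeds the efficacy stopping criterion in SAP 3.3, which uses an adjusted p-value for the primary outcome.

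**Working it through.** **1. The plan's own figure.** Inputs from SAP 3.2: 25 per arm, about 20% loss to death, design effect 1.12, SD 100, baseline mean 149, 70% improvement. Effective n per arm = 25 × 0.8 / 1.12 = 17.86. Effect = 0.70 × 149 = 104.3. Standard error = 100 × √(2/17.86) = 33.47. Drift = 104.3 / 33.47 = 3.117. At the tabled boundaries this gives power 0.795 for looks at 10/20/30/50 and 0.799 for four equal looks, against the stated 0.800. The final boundary is 2.397.

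**2. How often the trigger fires by chance.** For a continuous variable with m per arm, P(|SMD| > 0.2) = 2·P(t with 2m−2 df > 0.2/√(2/m)). For five independent variables, P(at least one) = 1 − (1 − p)^5. The count of five is an assumption; the SAP 5.4 list is longer.

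| m per arm | one variable | at least one of 5 |
|---|---|---|
| 5 | 0.760 | 0.999 |
| 10 | 0.660 | 0.995 |
| 15 | 0.588 | 0.988 |
| 25 | 0.483 | 0.963 |

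At 25 per arm, pairwise correlations of 0.3, 0.5 and 0.7 lower the last figure to 0.95, 0.93 and 0.88. A binary variable with prevalence 10-50% is flagged with probability 0.46-0.52. The expected number flagged is 0.483 × k: 2.4 of 5, 6.3 of 13, 9.7 of 20. Baseline P/F itself is not flagged in about 52% of trials.

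**3. Precision.** Null simulation at 25 per arm with k candidates, baseline P/F among them. Flagged variables enter a logistic propensity model with uncapped weights, and the estimate is the weighted difference in mean change. Assumed, because the documents do not give them: k; baseline SD 1, 0.5 or 0.3 times the 48-hour SD; correlation 0.3-0.7; and either no second predictor or one explaining a further 25% of variance. Entries are variance ratios; below 1 favours the first-named method.

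| Comparison | k=5 | k=10 | k=13 | k=20 |
|---|---|---|---|---|
| Weighting v unweighted change (only P/F prognostic) | 0.77-1.12 | 0.96-1.33 | 1.08-1.48 | 1.54-1.94 |
| Baseline covariate v weighting (only P/F prognostic) | 0.84-0.92 | 0.70-0.78 | 0.61-0.72 | 0.45-0.56 |
| Baseline covariate v weighting (second predictor unnamed) | 1.09-1.54 | 0.83-1.21 | 0.70-1.04 | 0.49-0.72 |
| Both covariates named v weighting (second predictor present) | 0.74-0.87 | 0.56-0.73 | 0.47-0.70 | 0.32-0.49 |

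With weights capped at 10, 13 candidates, correlation 0.5 and the second predictor unnamed, the third row becomes 0.95-1.01.

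**4. Baseline covariate against unweighted change.** With SD ratio s and correlation ρ the large-sample ratio is (1−ρ²)/(1+s²−2ρs). For s = 1 this is (1+ρ)/2: 0.65, 0.75, 0.85 at ρ = 0.3, 0.5, 0.7. For s = 0.5 and ρ = 0.5 it is 0.75/0.75 = 1.00, so no gain. Simulated ranges at n=50 were 0.65-0.87 for s = 1 and 0.76-1.03 for s = 0.5 or 0.3. A smaller s is plausible: entry below 150 limits the baseline SD to 150/2 = 75, or (150−44)/2 = 53 if the lowest value in the Protocol's SpO₂ table is the floor, against the planning SD of 100.

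**5. Does the choice change the decision?** At a single look with critical value 2.397, correlation 0.5 and effect 0.8 SD, weighted and unweighted results fell on opposite sides in 16% (5 candidates) to 20% (10 candidates) of simulated trials.

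**6. Type I error at that critical value.** Unweighted 0.020; triggered weighting with robust standard errors 0.012-0.018. Accepting either result gave 0.024-0.030. Model-based standard errors gave 0.013 and 0.027 for weighting alone with 5 and 10 candidates, and up to 0.038 for accepting either.

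**The case against.** The strongest reply is that the hierarchy can be read. SAP 6.3 makes weighting mandatory and SAP 6.4 places it inside the ITT mixed model, with as-treated and percent-change analyses as additions. If the trigger nearly always fires, the weighted ITT mixed model is the primary result in nearly every trial. That stands in part: the model class and population are stated. It does not settle which variables enter the weights, the conflict with the Protocol, or which result meets the boundary.

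A reader might infer that the rule inflates false positives. The material does not support this. With robust standard errors the rule as written was below the unweighted rate. The excess appears if either result may be accepted, which neither document proposes, or in the ten-candidate run with model-based standard errors, which neither document prescribes. Both documents also say that interpretation rests on effect sizes and confidence intervals.

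A reader might also infer that baseline P/F alone is always the better adjustment. It is not. With five candidates and a strong unnamed predictor, weighting is more precise. With 13 candidates and capped weights the two are about equal.

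The larger losses depend on how weighting is done. Uncapped weights and a logistic model holding every flagged variable are assumptions, and the Protocol's proviso about sample size could limit them. The variance grid used complete data and no hospital effect, so it approximates the planned mixed model.

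**Conclusion.** The point holds as a defect of specification. The SMD rule is near certain to fire (about 0.96 at 25 per arm with five assumed candidates, 0.88-0.95 if they are correlated), so chance and an open-label judgement choose the adjustment set. The SAP and Protocol rules conflict, and the result held to the Pocock boundary is not named as weighted or unweighted. The documents establish the last two without any of the simulation assumptions.

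The consequence is a data-dependent primary estimate and, in many settings, lost precision. The size of the loss rests on assumed candidate counts, SD ratios, correlations and weighting details. It would be too strong to say that the plan has no main analysis, that its error rate is inflated, or that a baseline covariate guarantees a gain: there may be none over unweighted change when the baseline SD is well below the 48-hour SD. This should be fixed; confidence is medium.

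**What to change.** By dated amendment, for the remaining looks and the final analysis, stating that the choice does not rest on first-interim data:

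1. Keep the planned mixed model with repeated measures and hospital effect. As the SAP notes of this model, "In addition, it tolerates missing observations". Add baseline P/F with its time interaction, and one other prognostic baseline variable named now, as fixed covariates with small-sample degrees of freedom such as Kenward-Roger.
2. Name this ITT between-group result as the one compared with the Pocock boundary.
3. Remove the SMD and clinical-judgement trigger, and the imbalance-dependent switch to relative change, from the primary analysis. Still report SMDs. Keep propensity weighting as a sensitivity analysis with a named variable list, a weight cap and robust variance.
4. Reconcile the Protocol's Statistical analysis section with SAP 6.3 and 6.4, and fix the outcome scale in advance. Otherwise the transformation and median-split rule in SAP 6.2 reopens the choice. On an untransformed scale the treatment effect is the same for 48-hour P/F and for change, so the primary outcome is unaltered.

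The degrees-of-freedom method matters. In simulations of the mixed model with baseline P/F as covariate, about 18% of 48-hour values missing by death, and 5 or 10 hospitals, type I error at nominal 5% was 4.6-6.2%, 5.0-6.0% and 4.2-5.6% at n = 20, 30 and 50 with Kenward-Roger, against 7.4-10.0%, 6.8-8.5% and 5.3-6.6% with a z test. This was not checked at the Pocock nominal levels of 0.015-0.017, and should be.

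Costs: no new data if the second variable is already collected; one degree of freedom per covariate per time point; other chance imbalances are described but not adjusted for; and the model changes after open-label first-interim results were seen. SAP version 4 postdates that analysis, so look 1 cannot be redone under the new rule.

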### 6.4. Outcomes comparison:

All analyses will be conducted initially as an intent-to-treat (patients are analyzed in the group they were randomized to), followed by an as-treated analysis. The primary outcome will be assessed within group and between groups. Differences in the primary outcome will be assessed using linear mixed models, with appropriate transformations if normality departure of residuals is detected. Linear mixed models allows us to adjust for potential confounders detected in the comparison of the groups at baseline using inverse probability weighting by a propensity score, the covariance structure, the repeated measures and the intra-hospital correlation (as this is a multicenter study). In addition, it tolerates missing observations. We will also compare percent change over baseline, using t-tests with the appropriate adjustment for heteroscedasticity if needed. Categorical outcomes will be compared using generalized estimating equations to account for confounders (as above), covariance structure and intra-hospital correlation. In addition, we will compare the “dose” of the intervention (i.e., how much of the treatment the patient received) as the effect of interest, as premature death is, unfortunately, expected. Survival analysis with inverse probability weighted Cox proportional hazards model and robust sandwich variance estimate with clustering for hospitals will be used for mortality and for survivor-bias outcomes censoring for death (e.g., thrombotic complication). As all outcomes are in-hospital, loss to follow-up is not likely. The pre-planned comparisons include within group (improvement over baseline) and between groups, all two-tailed with significance declared as defined by the Pocock spending method.

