### Section 3: Study Methods

**3.1. Trial design** Multicenter, pragmatic, randomized, open label, rapidly adaptive, controlled, clinical trial

The trial has a novel design with modified stepped-wedge and adaptive features in order to rapidly identify the intervention group with the highest chance of benefit. This unconventional design is appropriate for the current circumstances of the pandemic caused by a new, lethal and morbid virus infection (COVID-19) for which no known treatment exists. The below figure illustrates the design. In brief, the patients will be sequentially assigned to one of three following groups:

[figure not shown]
[figure not shown]
- Group tPA50 will receive 50 mg of tPA intravenous bolus administration over 2 hours, given as a 10 mg push followed by the remaining 40 mgs over a total time of 2 hrs (not to exceed 0.9mg/kg dose). Immediately following the tPA infusion, 5000 U of UFH will be delivered and the heparin drip will be continued to maintain the activated partial thromboplastin time at 60-80sec (2.0 to 2.5 times the upper limit of normal). This tPA protocol is a modification of the GUSTO I to III trials. 44,45
- Group tPA50 plus drip will receive 50 mg of tPA intravenous bolus administration over 2 hours, given as a 10 mg push followed by the remaining 40 mgs over a total time of 2 hrs (not to exceed 0.9mg/kg dose). Immediately following this initial tPA infusion, we will initiate a drip of 2 mg/hr tPA over the ensuing 24 hours (total 48 mg infusion) accompanied by an infusion of 500 U/hr heparin during the tPA drip. After this, heparin dose will be increased slowly to maintain a PTT between 60 and 80 sec, titrated per attending's discretion.
- Control: institution's protocol for ARDS

In order to rapidly accrue patients in one intervention group with a concurrent control, the first 10 patients will be randomly assigned to Group tPA50 or Control (Standard-of-care) when the first interim analysis occurs. If no stopping criteria are met, the next 10 patients are randomly

assigned to Group tPA50 or Control when the second interim analysis is done. If no criteria for stopping or dropping an arm are met, the next 10 patients are randomly assigned to Group tPA50 plus drip or Control when the third interim analysis is done. Finally, if no criteria for stopping or dropping an arm are met, the trial progresses with patients being randomized to Group tPA50 plus drip or Control up to the final analysis at n=50.

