### 3.2. Sample size

We anticipate that each of the five centers will enroll 8-12 patients. Sample size and power Analysis was conducted using Pass, vs 14.0 (NCSS, LLC, Kaysville, Utah, USA) and focused on the primary outcome as defined above.

Sample size assumptions:

- power=80%, confidence=95%, and 4 sequential tests(3 interim+1 final), using the Pocock spending function to determine test boundaries,
- potential improvement assumptions based on a previous study 40 with appropriate(e.g., Denver) altitude correction as well as mean baseline PaO2/FiO2=149 with an overestimated standard deviation of 100,
- design effect=1.12 due to the study's multicenter nature (intra-class correlation coefficient=0.03, average cluster=5);
- ~20% inflation to account for premature death

---

 Urbaniak, G. C., & Plous, S. (2013). Research Randomizer (Version 4.0) [Computer software]. Retrieved on April 10, 2020, at <http://www.randomizer.org/>

A sample size of 50 (25 in each intervention group and 25 in the control group) patients detects a >70% improvement in PaO2/FiO2 between intervention groups (both tPA50 and tPA 50 plus drip) and controls, and >91% improvement in PaO2/FiO2 between intervention tPA 50 plus drip) and controls. Recruitment will assume at least 30% increase to account for refusal or inability to consent.

**Consent: We anticipate consenting enough patients to result in 50 eligible patients, thus we plan on a max of 60, to be re-evaluated during each of the interim analyses. LAR, as defined by the state and institutions legislation/policies, will be able to consent.**

The table below shows the details of the interim analyses with the Pocock spending method:

Look	N of Patients	Lower Bndry	Upper Bndry	Nominal Alpha	Inc Alpha	Total Alpha	Inc Power	Total Power
1	10	-2.43798	2.43798	0.015	0.015	0.015	0.18976	0.190
2	20	-2.42677	2.42677	0.015	0.011	0.026	0.25179	0.442
3	30	-2.41014	2.41014	0.016	0.009	0.035	0.21191	0.653
4	50	-2.39658	2.39658	0.017	0.008	0.043	0.14655	0.800

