## Section 4: Statistical Principles

**4.1. Level of statistical significance:** see above description of p-value for interim analyses.

**4.2. Description and rationale for any adjustment for multiplicity of time points:** There will be no adjustment for multiple outcomes, as all were pre-planned. The investigator-statistician in charge ([name]) strongly agrees with the argument that adjustment for multiple comparisons in pre-planned hypotheses leads to more type II errors.

**4.3. Analysis populations:** all analyses, including safety analyses, will be conducted initially as **intention-to-treat** and then **as-treated**.

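### Regimen is tied to enrolment stage, but SAP 6.4 has no stage term and no rule on which controls the drip is compared with, and two unranked primary-outcome contrasts share one Pocock table

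*SAP*

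**What the plan says.** SAP 3.1 randomises the first 20 patients, in two steps of 10, to tPA50 or control, and the next 10 to tPA50 plus drip or control. After that, "the trial progresses with patients being randomized to Group tPA50 plus drip or Control up to the final analysis at n=50". Under the 11/5/2020 amendment the switch depends on results at 20 patients: if PaO2/FiO2 at 48 hours improves by at least 50%, tPA50 continues to the end and no drip arm is opened.

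For the analysis, SAP 6.4 says "Differences in the primary outcome will be assessed using linear mixed models". The adjustments it names are propensity weighting for baseline differences, the covariance structure, repeated measures and hospital. Enrolment stage is not among them. Comparisons within and between groups are "all two-tailed with significance declared as defined by the Pocock spending method".

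SAP 3.2 (Sample size) assumes "power=80%, confidence=95%, and 4 sequential tests(3 interim+1 final), using the Pocock spending function to determine test boundaries". It states "A sample size of 50 (25 in each intervention group and 25 in the control group") and gives two detectable effects: more than 70% for both tPA regimens together v control, and more than 91% for the drip alone v control. One boundary table follows, with looks at 10, 20, 30 and 50 patients. SAP 4.2 says "There will be no adjustment for multiple outcomes, as all were pre-planned". The protocol's Statistical analysis section sets the final overall significance level at p<0.05, two-tailed.

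**The concern.** No drip patient is randomised alongside the roughly 10 controls enrolled in the first two stages. If those controls enter the drip comparison without a stage term, a change over time in outcome becomes part of the estimated drip effect. The documents themselves foresee such change: entry criteria may be modified at interim analyses (SAP 3.4), co-enrolment in other COVID-19 trials is allowed (protocol, after the inclusion criteria), and the protocol's timeline starts with core institutions and adds others later.

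The second issue is error control. Two treatment contrasts on the primary outcome can each be declared positive at the same boundaries. The efficacy stopping rule in SAP 3.3 refers to the primary outcome without saying which contrast it means. From the third look on, a stopping decision could therefore rest on either, and the overall 5% would not cover both.

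**Working it through.** **Inputs.** From SAP 3.2: SD 100, baseline mean 149, design effect 1.12, about 20% loss to death, and boundaries |Z| = 2.43798, 2.42677, 2.41014, 2.39658. From SAP 3.1, with 1:1 allocation: 5, 5, 5 and 10 patients per arm per stage. That gives 25 controls and 25 tPA patients (10 tPA50, 15 drip), with 15 controls concurrent with the drip.

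**Reproducing the plan's detectable effects.** The drift that gives 80% power at the tabled boundaries is 3.118 (equally spaced looks, which also reproduce the table's cumulative powers). Then

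detectable % = 3.118 × 100 × √(1/n₁ + 1/n₂) × √1.12 / 149, with n after 20% loss.

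- Pooled, 25 v 25 → 20 v 20: 311.8 × 0.3162 × 1.0583 / 149 = 70.0%. The plan says 70%.
- Drip, 15 v 15 concurrent → 12 v 12: 311.8 × 0.4082 × 1.0583 / 149 = 90.4%. The plan says 91%.
- Drip, 15 v all 25 controls → 12 v 20: 311.8 × 0.3651 × 1.0583 / 149 = 80.9%. This does not match.

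With looks at 10/20/30/50 of 50 the drift is 3.135, and the three figures become 70.4%, 90.9% and 81.3%. The conclusion is the same.

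**Arm sizes.** Two intervention groups of 25 plus 25 controls would be 75. A total of 50 fits only 25 on any tPA and 25 controls, which is also what reproduces the 70%.

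**Bias if all controls were used.** At the final look 10 of 25 controls are non-concurrent. If the outcome level shifts by d between the two periods, drip v control is biased by (10/25)d = 0.4d. The documents give no value for d. As assumptions, d = 20 gives a bias of 8 and d = 40 gives 16. These are 0.08 and 0.16 of the SD, or 8/135.6 = 6% and 16/135.6 = 12% of the planned drip effect (0.91 × 149 = 135.6). Baseline weighting may remove part of this.

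**False-positive rates with no true effect.** Simulated with the tabled boundaries, pooled at all four looks and drip at looks 3 and 4, because looks 1 and 2 contain no drip data:

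| | concurrent controls | all controls, d = 0 | all controls, d = 20 | all controls, d = 40 |
|---|---|---|---|---|
| pooled | 4.5% | 4.5% | 4.5% | 4.5% |
| drip | 3.0% | 2.9% | 3.3% | 4.6% |
| at least one | 6.7% | 6.4% | 6.7% | 8.0% |

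The concurrent column does not change with d.

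**Balance within stage.** Blocks of 10 run within hospital (SAP 3.2, Randomization details). If, as an assumption, each of five hospitals had contributed four of the first 20 patients, an exact 10:10 split at the switch would occur in 22% of cases, and 12:8 or worse in 41%.

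**The case against.** A reader might infer that the SAP prescribes all 25 controls for the drip comparison. It does not. SAP 6.4 is silent, SAP 3.1 gives accrual alongside a concurrent control as the purpose of the staging, and the 91% figure reproduces only with concurrent controls. This is an unwritten rule, not a specified biased analysis.

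A reader might also infer that any change over time biases the results in general. That is too broad. The pooled contrast is not systematically biased when allocation is 1:1 within stage. SAP 6.3 weights for clinically relevant baseline differences or an absolute SMD above 0.2, over a wide baseline set (SAP 5.4), and the model accounts for hospital. What remains is unmeasured drift, changes in care after randomisation, and chance imbalance where hospital blocks straddle the switch. With the assumed shifts of 20 and 40, the drip test alone stays below 5% at the tabled boundaries.

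On error control, the two contrasts share patients (correlation 0.775 with concurrent controls, 0.866 with all), so it would be wrong to describe the error as doubled to about 10%. Early efficacy stopping also requires a secondary outcome, and SAP 3.2 argues against a rigid 0.05 cutoff in favour of estimates with intervals. Both points soften the consequence. They do not remove the stated overall 5%. The waiver in SAP 4.2 concerns multiple outcomes, so it neither permits nor rules out two treatment contrasts.

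Finally, if tPA50 continues to 50 patients there is no drip arm and neither issue arises.

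**Conclusion.** The point holds in limited form. Two statements are wrong as written. The overall 5% is exceeded if either contrast may be declared positive at the tabled boundaries (about 6.4-6.7%, with no period shift or with concurrent controls), and the arm sizes as worded do not add to 50.

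The missing stage term and the missing concurrent-control rule are omissions that are cheap to repair. Their size depends on an unknown shift d: a bias of 0.4d in drip v control at the final look, only if all controls were used, and before whatever baseline weighting removes.

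These figures assume 1:1 allocation within stage, the planned 10/10/10/20 sequence with the drip deployed from patient 21, and the plan's own SD, loss and design effect.

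**What to change.** 1. In SAP 6.4, limit drip v control to controls randomised in the same stages. This costs none of the planned power, because the stated 91% already corresponds to 15 v 15.
2. Add a two-level stage term (before/after the regimen switch) to the primary mixed model, at a cost of about one degree of freedom. Use it in the GEE and Cox models only where the data allow, since ten sites are listed for 50 patients and strata may be sparse.
3. Before the next look, name one primary contrast for the Pocock boundaries and the efficacy stopping rule. The choice is the sponsor's. Pooled tPA v control, for example, matches the existing table. The other contrast can be secondary with a confidence interval, or tested second in a fixed order with its own boundary. With looks at 1/3 and all of the drip information and its own 0.05 spend, the drip's detectable effect is about 85% taken alone. Splitting alpha 0.025 + 0.025 would instead give about 74.8% pooled and 93.5% drip.
4. Restate the planned arms as 25 control and 25 tPA, of which about 10 tPA50 and 15 drip if the drip is deployed.

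All four are changes to SAP text (the fourth also to the protocol's sample-size sentence), with no effect on enrolment or data collection.
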